7.1. Inclusion Criteria

1. Patients with suspected pancreatic malignancy as defined by one or more of;
 - a) Focal lesion in the pancreas/bulky pancreas/dilated pancreatic duct (+/- metastases) detected on Multidetector CT scan (+/- MRI/EUS/USS)
 - b) Jaundice due to distal obstruction of the common bile duct or ampulla (not due to calculi) defined as serum bilirubin. 35 µmol/l
 - c) Serum CA19.9 value above 37KU/l
2. Able to attend for PET/CT scan
3. Able to undergo Multidetector CT scan
4. Able to attend for up to 12 months follow-up
5. Fully informed written consent given.

7.2. Exclusion Criteria

1. Patients younger than 18 years
2. Pregnancy
3. Patients with poorly controlled diabetes

7.3. Patient Withdrawal from Study Intervention

In consenting to the study, patients are consenting to all study procedures, follow-up, and data collection. If voluntary withdrawal from intervention occurs, the patient should be asked to allow continuation of scheduled evaluations, complete an end-of-study evaluation, and be given appropriate care under medical supervision.

Patients may be withdrawn from the study for any of the following reasons:

- a. Patient/Legal representative withdraws consent.
- b. Intercurrent illness preventing further follow-up
- c. Any change in the patient's condition that justifies the withdrawal of the patient in the clinician's opinion.

If a patient wishes to withdraw from the study, centres should nevertheless explain the importance of remaining on study follow-up, or failing this, of allowing routine follow-up data to be used for study purposes. Generally, follow-up will continue unless the patient explicitly also withdraws consent for follow-up (section 7.5).

7.4. Patient Transfer

For patients moving from the area, every effort should be made for the patient to be followed-up at another participating study centre and for this study centre to take over responsibility for the patient or for follow-up via GP. A copy of the patient CRFs should be provided to the new site. The patient will have to sign a new consent form at the new site, and until this occurs, the patient remains the responsibility of the original centre. The LCTU should be notified in writing of patient transfers.

7.5. Withdrawal from Study Completely

Patients who autonomously withdraw from the study for reasons other than those listed above, have previously consented to follow-up in the study. Data up to this time can be included in the study if anonymised. Such patients may need to reaffirm that they consent to follow-up through usual National Health Service (NHS) mechanisms. If the patient explicitly states their wish not to contribute further data to the study, the LCTU should be informed in writing by the responsible physician and an end of study CRF should be completed.

7.6. Loss to Follow-up

If any of the study patients are lost to follow up, contact will initially be attempted through the PI at each centre. If the PI at the study centre is not the patient's usual clinician responsible for their speciality care then follow-up will also be attempted through this clinician. Where all of these attempts are unsuccessful, the patient's GP will be asked to provide follow-up information to the recruiting centre.

7.7. Co-enrolment Guidelines

Patients registered for the PET-PANC study are not restricted to entry onto any other clinical trials, studies or research projects. However information regarding any trial participation will be collected on the follow-up CRF forms.

8. Screening And Registration

8.1. Screening

Screening and Identification of eligible patients will take place at the research site's pancreatic MDT meeting typically consisting of surgeons, gastroenterologists, radiologists, oncologists, pathologists and nurses. Patients must have undergone standard evaluation: multidetector CT +/- other modalities, e.g. EUS. The patients should be reviewed at the MDT meeting as per standard protocol for that centre. Eligible patients for this study will include all patients with suspected pancreatic malignancy as defined in the inclusion criteria.

The decision on patient eligibility by the pancreatic MDT should take into account all clinical details and investigations undertaken for the patient under discussion. Multidetector CT with pancreas-specific protocols will be used as the standard for diagnosis in all centres. The number of lesions, size of lesions, morphological features (solid, cystic), any dilation of the bile duct and or pancreatic duct, vascular involvement and any extra-pancreatic disease will be recorded on the D1 CRF after patient registration.

If the patient is deemed eligible they will be reviewed in the outpatient clinic or as an inpatient and provided with a patient information sheet (Appendix A). Informed consent will be obtained after the patient has had sufficient time (at least 24 hours) to make a decision and prior to any baseline assessment and study registration. The diagnosis, stage and management plan from the MDT meeting will be recorded in the CRF as D1 at that point.

A log of all potential patients will be kept, including individuals who decide not to participate in or who are found to be unsuitable for the study. The LCTU will provide a 'Screening and Registration' log to each centre at the point of initiation

8.2. Study Registration

For patients who have given informed consent and have been found to comply with all inclusion and exclusion criteria, the responsible clinician or delegate will contact the LCTU to register the patient. To ensure essential entry criteria are fulfilled, registration can only occur following the completion and forwarding of the study **REGISTRATION FORM** and **SIGNED INFORMED CONSENT FORM** by the investigators:

The registration documents should be faxed to the LCTU on Monday – Friday from 09:00 to 17:00, [contact]. Prior to faxing documents, site staff should telephone the study co-ordinator to inform them of the incoming registration fax.

Personnel from the LCTU will review the registration form, confirm eligibility and record essential demographic data. The Registration Form will be annotated with details of the unique study number allocated to the patient. The unique study number and date of entry into the study must then be recorded on the original Patient Screening & Registration Log and in the patient case notes. The original copy of the consent form will be retained in the patient's medical notes and must be available for inspection.

9. Assessments and Procedures

9.1. Schedule of assessments

Procedures	Screening (MDT)* ♦	Baseline (Day 0)*	D1	Additional Pet/CT	D2	D3 – Actual Management	Follow-Up Schedule					D4 – Reference Standard
							12 weeks	24 weeks	36 weeks	48 weeks/ Study Completion	Premature Discontinuation	
Window for time points (All visit time points are from the Day 0 Baseline visit)				2 weeks ± 4 days			± 2 weeks	± 2 weeks	± 2 weeks	± 2 weeks		
Signed Consent Form		X										
Assessment of Eligibility Criteria	X	X										
Review of Medical History & Demography		X										
MDCT (± MRI/EUS/USS/ERCP)	X*♦	X♦										
Review of Concomitant Medications		X					X	X	X	X	X	
Urine pregnancy test (WCBA) ■		X										
Random blood glucose		X										
PET/CT Scan				X								
CA.19.9	X♦	X♦					X♦	X♦	X♦	X♦		
EQ-5D Quality of Life		X					X	X	X	X		
CSRI form		X					X	X	X	X		
WHO Performance Status		X					X	X	X	X		
Physical Exam	Complete	X										
	Symptom-Directed	X					X	X	X	X		
Assessment of Adverse Events				X								
Clinical Laboratory^	Chemistry U &Es LFT CRP Amylase	X♦	X♦				X♦	X♦	X♦	X♦		
	Haematology FBC Clotting Profile	X♦	X♦				X♦	X♦	X♦	X♦		
Record Diagnosis, management plan and staging			X		X	X						
Reference standard												X

* The patient may have results from one or all of the marked procedures

♦ Procedures carried out according to local practice with regard to patients with suspected pancreatic malignancy, these are not study-specific procedures.

■ Only to be conducted in women of child bearing age (WCBA)

9.2. Screening for study eligibility

Patients will be assessed for their eligibility for entry into the study during the local MDT meeting. Screened patients should have a suspected pancreatic malignancy with one or more of the following exploratory test completed to be considered for the study:

- Multidetector CT scan
- Serum bilirubin test
- Serum CA 19.9 test

The patient management plan and clinical decisions made at this point will be documented on the D1 CRF.

9.3. Baseline assessments

After patients have consented to study participation and signed the informed consent form, baseline assessments should be performed prior to study registration in order to confirm eligibility. The PET/CT scan should be performed within 2 weeks (\pm 4 days) of the baseline visit. This is to ensure patients are not delayed in their diagnostic and management pathway due to participation in the study. The baseline assessments include the following:

- Informed Consent – taken prior to any other study procedures
- Assessment of eligibility criteria
- Review of medical history & demography
- Review of concomitant medications
- EQ-5D Quality of Life
- WHO performance status
- Physical exam (complete and symptom-directed)
- CSRI questionnaire
- Urine pregnancy test (WCBA)
- Random blood glucose

The patients will undergo the following investigations according to standard clinical practice:

Clinical Laboratory

Chemistry

- U & Es (i.e. urea and electrolytes)
- LFT
- CRP
- Amylase
- CA.19.9

Haematology

- FBC
- Clotting Profile

Further diagnostic investigations including:

- Multidetector Computed Tomography (MDCT)
- Endoscopic Ultrasound (EUS)
- Endoscopic Retrograde Cholangiopancreatography (ERCP)
- Magnetic Resonance Cholangiopancreatography (MRCP)

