4.6. Potential Risks and Benefits

This study will assess the effects of adding PET/CT to the usual standard of care for patients with suspected pancreatic cancer. The main risks will be of the PET/CT itself and any possible delay to the patients diagnostic and management pathway. The risks of PET/CT scan are related to the radiotracer ^{18}F -FDG itself, allergic reaction to the radiotracer and radiation exposure from the CT scan. Allergic reactions to radiopharmaceuticals may occur but are extremely rare and are usually mild. The doses of radiotracer administered are small typically 8mSv for adults using 400MBq. The radiation dose from the CT scan can be low (e.g. an effective dose of about 7mSv) The risk of increased carcinogenesis associated with radiation exposure is outweighed by the benefits of correctly identifying patients who will can undergo surgery and also preventing unnecessary surgery in others. The scans will be performed in a timely manner to minimize any delay.

5. Selection of Centres/Clinicians

The study will be carried out in major pancreatic centres with annual referrals of over 100 pancreatic patients per year.

Each participating Centre (and investigator) has been identified on the basis of:

- Being a major pancreatic centre with annual referrals of over 100 pancreatic patients per year
- Conduct of pancreatic/hepatobiliary Multidisciplinary Team (MDT) meetings consisting of surgeons, gastroenterologists, radiologists, oncologists and pathologists.
- A lead clinician with a specific interest in, and responsibility for, supervising and managing patients with pancreatic disease
- Having a radiologist to act as co-investigator who is ARSAC registered
- Showing enthusiasm to participate in the study.
- Ensuring that sufficient time, staff and adequate facilities are available for the study.
- Providing information to all supporting staff members involved with the study or with other elements of the patients management.
- Access to a PET/CT scanner and the ability and willingness to send scans for central review.
- Acknowledging and agreeing to conform to the administrative and ethical requirements and responsibilities of the study, including signing up to Good Clinical Practice (GCP) and other regulatory documentation.

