9.4. PET/CT

The patients will then undergo FDG PET/CT scanning within two weeks following consent and baseline visit(s). Should the PET/CT scan not be conducted within two weeks the LCTU should be informed. If the

research site deems the resulting delay in patient management to be unacceptable the patient should be withdrawn from the study and the LCTU informed of this decision.

The PET/CT scan result will first be documented independently of other clinical information. The patient will then be discussed again by the investigator or at the MDT with the results of the PET/CT available. The management decision will be documented at this point D2 (see section 10.2).

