Appendix G: PET/CT PROTOCOL

1 Patients

- Patients with diabetes mellitus either type 1 or type 2 must be well controlled with a fasting blood glucose not exceeding 10.0mmol/l.
- Specific guidelines for patients with either type 1 or type 2 diabetes mellitus as follows;

Type 1 - insulin dependent diabetes mellitus (requires injections) and Type 2 - diabetes mellitus (requires oral anti-diabetic drugs such as Metformin or pioglitazone)

Arrange for the patient to have an appointment at 12 midday where practicably possible

- Instruct patient to eat breakfast at 6am and have their normal dose of Insulin/medication at this time, and then only drink water.
- The patient should not have any more insulin/diabetes medication until after the scan.
- Instruct patient to bring something with them to eat straight after the scan.
- Instruct patient to bring their insulin/diabetes medication with them.
- Instruct patient to bring any emergency medication they have been issued with.
- If a midday appointment cannot be arranged then instruct the patient to eat and take insulin/medication 6 hours prior to the appointment time.
- Do not encourage the patient to starve for more than 6 hours prior to the appointment

Type 2 - diabetes mellitus controlled by diet

- Determine from patient when their blood sugar level is normally lowest. Book the appointment at this time if possible.
- Instruct the patient to eat 6 hours prior to the appointment time and then starve and just drink water until after their appointment.
- Instruct the patient to bring something with them to eat straight after the scan.

2 Preparation:

- Patients to fast for 6 hours prior to scan.
- Patients weighed without shoes and coats (ensure calibrated class III device with requirements defined in the Non-Automatic Weighing Instruments Directive 2003).
- Blood glucose monitored using BM Glucometer (ensure calibrated device).
- Patients to drink 2-3 glasses of water prior to test to ensure hydration.
- Metal denture fixtures etc to be removed whenever possible (CT artefacts).

3 Injection:

- FDG injected via butterfly cannula under quiet conditions.
- Patient to remain silent.
- FOR 2D scanning inject 350-530MBq. Important must ask the ARSAC holder for approval above 400MBq (ARSAC DRL) for any patients.
- FOR 3D scanning inject 150-350MBq
-
- Measure syringe residue and reduce injected activity accordingly.

4 Uptake:

- Patient to remain quiet and inactive during uptake at room temp.

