- Patient to empty bladder just prior to positioning on scanner bed.
- Emission scan must start at 90 minutes post injection.

5 Positioning:

- Patient to be scanned on regular couch top.
- Begin scanning at the groin and end at the base of the orbits.
- Scan with arms up if a single whole body scan is performed.

6 Acquisition Parameters:

- Use routine local protocols

7 Reconstruction Parameters:

- OSEM with CT for attenuation correction using local routine parameters.

8 Local Archive

- Reconstructed CT, PET AC and PET NAC data MUST be archived locally. Raw data to be archived according to local protocol.

9 Quality Assurance and Control:

- Under agreed QA and QC protocols using suitable phantom and anonymised test patient scans etc.
- Ensure accurate SUV are recorded for study

10 PET/CT data transfer to the Core Lab:

Under agreed protocol transfer following reconstructed and anonymised files

- CT
- PET AC
- PET NAC
- PET/CT report from local imaging team

11 Local reporting of PET/CT

- A report will be made by the imaging team in the local hospital. The image data together with the report will be transferred to the central laboratory using agreed protocols.
- Local and central reports as a minimum requirement shall assess the following with SUV max values quoted where applicable;
 - Pancreatic lesion
 - Lymph nodes
 - Metastases
 - Synchronous lesions
- PET/CT will be reviewed by an expert in clinical PET/CT, independent of the report from the local hospital.

- Any differences between the local hospital and the central laboratory will be resolved by consensus with the local hospital team.
- Standardised criterion will be used for reporting the scans.

12 Data Transfer to Core Lab

- Procedures must be in place to ensure image data is sent to the PET/CT Core Lab promptly to allow central reporting to fit in with any patient treatment schedules.
- All image files must be compliant with DICOM PART 10 format.
- An agreed, tested and secure method must be used to transfer anonymised data between scanning facilities and the PET/CT Core Lab.
- All files must be clearly named using a pre-arranged filename convention
- Named persons (and their deputies) should be identified with responsibility for scanning, QC and data transfer at participating PET/CT centres.

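### Pregnancy is tested only at Day 0, the visible protocol requires no check on the scan day, and the 24-hour reporting limit shuts out the birth-defect category the protocol defines

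*Protocol*

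**What the plan says.** Section 7.2 excludes pregnant patients. Section 9.3 lists "Urine pregnancy test (WCBA" among the baseline assessments and gives their purpose: "baseline assessments should be performed prior to study registration in order to confirm eligibility". The schedule in 9.1 restricts the test to women of child-bearing age and marks it once, under Baseline (Day 0).

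The scan follows later. In 9.1 its window is two weeks plus or minus four days, and "All visit time points are from the Day 0 Baseline visit". Section 9.3 also allows the four days. Section 9.4 is tighter: "The patients will then undergo FDG PET/CT scanning within two weeks following consent and baseline visit(s"). If that limit is missed, 9.4 asks the site to inform the LCTU, and the patient is withdrawn only if the site finds the resulting delay unacceptable.

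For the scan day, the PET/CT column of 9.1 carries only the scan and the adverse event assessment. Appendix G, part 2, opens with "Patients to fast for 6 hours prior to scan" and goes on to weight, blood glucose, hydration and removal of metal. Part 5 sets the field: "Begin scanning at the groin and end at the base of the orbits". Section 4.6 describes the exposure: "The doses of radiotracer administered are small typically 8mSv for adults using 400MBq", plus a CT component that can be low, for example "an effective dose of about 7mSv".

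On safety reporting, 15.1(e) counts a congenital anomaly or birth defect as a serious adverse event. Section 15.2 confines adverse event recording and serious adverse event reporting to the 24 hours after the scan and releases sites from reporting anything later.

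**The concern.** The exclusion protects against irradiation at the scan, but it is verified only at an earlier visit. A Day 0 test is the right tool for confirming eligibility at registration. It says nothing about a conception between Day 0 and the scan, and it can miss one that is very recent at Day 0.

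The reporting rule has a related weakness. The protocol defines a seriousness category that could apply only long after the scan, then closes reporting one day after the scan. If an exposed pregnancy came to light later, section 15 would not bring its outcome to the trials unit. It would also not reach the parties named in 15.5 (the ARSAC certificate holder, the radiopharmacy and the sponsor).

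What is at stake is the safety of a probably small number of women. No estimate or test in section 12 depends on it.

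**Working it through.** There is no sample-size or error-rate figure to reproduce. The check is day arithmetic plus a comparison of sections.

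**1. Interval from test to scan**

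| Source | Rule | Days from Day 0 |
|---|---|---|
| 9.4 | within two weeks | at most 2 × 7 = 14 |
| 9.1 | two weeks ± 4 days | 14 − 4 = 10 to 14 + 4 = 18 |
| 9.3 | within two weeks (± 4 days) | latest 14 + 4 = 18 |

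These are nominal limits. Section 9.4 answers a later scan with a notice to the LCTU, so no text sets an absolute maximum. Sections 9.3 and 9.4 also permit a short interval.

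**2. What is rechecked on the scan day**

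Two exclusions in 7.2 can change between Day 0 and the scan.
- Diabetes control: random glucose at baseline (9.1, 9.3), then glucose again before the scan, with a fasting limit of 10.0 mmol/l for patients with diabetes (Appendix G, parts 1 and 2).
- Pregnancy: urine test at baseline (9.1, 9.3), then nothing in the visible text.

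**3. Exposure as the protocol states it**

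From 4.6, 8 mSv (FDG at 400 MBq) + 7 mSv (CT, low-dose example) = 15 mSv adult effective dose. The documents give no fetal dose, and none is inferred here.

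**4. Category (e) against the 24-hour limit**

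15.1(e) requires an anomaly or birth defect to have been found. 15.2 requires the event to occur within 24 hours of the scan. For a pregnancy unrecognised at the scan, both conditions cannot realistically be met. The onward route in 15.5 starts from a serious adverse event, so it is not triggered either.

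**5. Other routes, case by case**

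- *Pregnancy recognised before the scan.* Covered. Sections 7.3(c) and 16.1 allow withdrawal, 16.1 has the reason recorded, and 19.4.7 checks that it was.
- *Pregnancy already present at registration, recognised after the scan.* This breaches 7.2 and can be logged under 19.4.6. That route reaches the Chief Investigator, the ISDMC and the co-sponsors. It does not ask for the pregnancy's outcome.
- *Conception after Day 0, recognised after the scan.* The patient met 7.2 when registered, so this is not clearly a violation under 19.4.6. The follow-up forms in 9.5 record outcomes in general for 12 months but do not name pregnancy.

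**6. Effect of the change**

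With an enquiry before FDG injection, the interval between the last required check and the exposure falls from nominally 14 or 18 days to 0 days. The added sentence in 15.2 covers the second and third cases in step 5.

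**The case against.** The strongest reply is that nothing here is wrong on its face. Pregnancy is excluded, it is tested for, and the test sits where eligibility is decided, so a second check is a preference. Other controls also surround the scan. Each centre needs an ARSAC research certificate (2.3) and an ARSAC-registered radiologist as co-investigator (5), the study runs under the 1978 radioactive substances regulations (2.2), and a separate PET/CT quality document exists but is not shown (6.3). Appendices A and B are not shown either. A PET centre may well ask about pregnancy as routine.

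Much of this stands. A reader might infer that women are scanned without any check. The documents do not support that: they show only that the visible protocol does not require one. A reader might also infer that an exposed pregnancy would go entirely unreported. That is too broad, because 19.4.6 gives a route for a pregnancy present at registration.

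The reply does not remove the point. The protocol itself fixes the scan-day list and rechecks glucose on it. It covers up to 30 sites (3) and both fixed and mobile scanners (11.2), which is a reason not to rely on unstated local habit. The conflict between 15.1(e) and 15.2 lies within the document and does not depend on local practice.

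**Conclusion.** The point holds as a cheap improvement in patient safety, of low weight. Pregnancy status is verified only at Day 0, nominally up to 14 days (9.4) or 18 days (9.1, 9.3) before an exposure of about 15 mSv as stated. The visible text does not require it to be confirmed on the scan day. Category (e) of 15.1 cannot in practice produce a report under 15.2. Conception after Day 0 is not clearly caught by 19.4.6, and no pregnancy outcome is requested in any case.

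Three further readings are tempting but unsupported:
- That 14 or 18 days is a ceiling, or that a scan after day 18 is automatically a recorded deviation. Section 9.4 sets no hard limit, and 19.4.6 names no day.
- That the share of exposures prevented can be quantified. The documents give neither how early the urine test turns positive nor the yield of an enquiry.
- That a fetal risk has been shown. Only adult doses are stated.

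The conclusion assumes that the pages not shown contain no such requirement. The low weight assumes that few women of child-bearing age will be enrolled; the documents give no number. The primary analysis is unaffected.

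**What to change.** Keep the Day 0 urine test for eligibility and make two additions.

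1. In the PET/CT column of 9.1 and in Appendix G, part 2: *For women of child-bearing age, pregnancy status is confirmed by enquiry on the scan day before FDG injection, with a repeat urine test if there is any doubt.*

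2. In 15.2: *Any pregnancy found to have been present at the scan, and any resulting category (e) event, is reported to the LCTU when the site learns of it, regardless of the 24-hour limit.*

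The cost is a brief enquiry and an occasional urine test in what are probably few women, with no extra staff. The remaining limitation is that a very early conception can still be missed by both enquiry and test. The reporting sentence is there for that case.
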